### **PROCEDURES**

# **Research Design**

Patients from the high-risk sample (primary target population) will be randomly assigned to one of 4 study arms. Outcomes during the 2020-2021 flu season will be compared between study arms

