Question 3: Patients in each of the conditions were stratified based on whether they were in the top 3rd percentile of risk, or in the subsequent 3rd-10th percentile. Patients in the former group were always told they were in the "top 3%" of risk. Patients in the latter group were either told they were in the "top 10%" of risk or that they were at "high" risk. These different risk conditions will be used to ask whether a) patients with the same risk level are affected by a vague verbal ("high") vs. specific numeric ("top x%") risk framing and b) patients with the same numeric risk phrasing are differentially affected due to different specific risk levels (3% vs. 10%). Analysis 3: We will evaluate this using a single logistic regression model with "top 10%" condition dummy coded as the reference level. This will allow the contrasts of "top 10%" vs. "high" (for question 3a) and of "top 10%" vs. "top 3%" (for question 3b).

Secondary Analyses:

We will use the approaches in Analyses 1 and 2 to evaluate the impact of the intervention on the secondary outcome measures listed in the pre-registration.

Exploratory Analyses

Impact on timing of shot

This analysis will focus on the subgroup of patients who were vaccinated. We will employ linear regression models to compare the time it took to receive a flu shot for patients who were informed about their risk status with those in the control group (as in Analysis 1) and among the 3 risk status communication conditions (as in Analysis 2). Time will be specified as the number of days since the beginning of the intervention (September 21, 2020). If the distribution of the time variable is skewed so as to violate the assumptions of a linear regression, data will be log transformed or analyzed using a gamma model.

Impact of age

While older patients tend to be aware of their increased vulnerability, younger patients may be more surprised to learn of their high-risk status. We will therefore examine the differential response of patients above vs. below age 65 by introducing this age variable as moderator and assessing if it interacts with experimental group to affect vaccination behavior. We will also conduct this analysis using age as a continuous variable.

Impact of modality

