Patients who received an intervention message (groups 2, 3, and 4) may have received communications via up to 3 modalities. We will employ logistic regression to evaluate the impact of modality on outcomes of interest, assessing pairwise comparisons of the following modality combinations: letter only, letter + myGeisinger, letter + SMS, or letter + myGeisinger + SMS. The small number of patients who did not experience one of these modality combinations will be excluded for this analysis.

Impact of risk level and framing

We will evaluate the impact of risk level (top 3rd percentile vs. remaining 3-10th percentile) as a moderator for Analysis 1 and risk framing ("top 3%", "top 10%", "high") as a moderator for Analysis 2, assessing if the moderators interact with experimental group to affect study outcomes. As described in Analysis 3, risk framing will be dummy coded with "top 10%" as the reference level.

Analysis Exclusion Criteria

A small number of deceased patients and patients who received the flu vaccination before the start of the intervention were unintentionally included in this study. These patients will be

excluded from all analyses. Another small population of patients' print letters were returned to sender; these patients will remain included in analyses but will be documented as having not been contacted through this modality. Finally, due to delays in intervention rollout, there were patients who were vaccinated prior to the start of the study (9/21/20). These patients will be excluded from all above analyses, as they were not intended to receive the intervention.

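### Primary contrast 3b sets the top-3% wording against the top-10% wording across two risk strata with no control reference, so it mixes any baseline stratum difference with any difference in message effect

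*SAP*

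**What the plan says.** Randomisation is described in the protocol under Research Design: "Patients from the high-risk sample (primary target population) will be randomly assigned to one of 4 study arms". The arms are a control and three types of message.

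The SAP, Question 3, adds a second layer: "Patients in each of the conditions were stratified based on whether they were in the top 3rd percentile of risk" or in the 3rd-10th percentile band. Of the top stratum it says "Patients in the former group were always told they were in the" top 3%. Of the lower stratum it says "Patients in the latter group were either told they were in the" top 10%, or else at 'high' risk with no number. Question 3a compares the two wordings used in the lower stratum. Question 3b asks whether "patients with the same numeric risk phrasing are differentially affected due to different specific risk levels (3% vs. 10"%).

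Analysis 3 covers both: "We will evaluate this using a single logistic regression model with" the top-10% wording as reference level. Contrast 3b is read from the top-3% dummy. No control comparison and no covariate is named.

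Two related analyses appear under Exploratory Analyses, Impact of risk level and framing. The first is "We will evaluate the impact of risk level (top 3rd percentile vs. remaining 3-10th percentile) as a moderator for Analysis 1". The second takes the risk framing "as a moderator for Analysis 2, assessing if the moderators interact with experimental group to affect study outcomes". Neither is linked to question 3b.

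**The concern.** The top-3% and top-10% wordings never occur in the same stratum, so in contrast 3b wording and stratum are one variable. Stratum is fixed by predicted risk of flu complications. Patients at different predicted risk may differ in vaccination or flu diagnosis whatever message they receive, and the plan gives no reason to assume that they do not.

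The contrast is primary and its question is causal. If the strata differ at baseline, a significant 3b could be that difference alone. A null 3b could be a baseline gap cancelling a real difference in response. Neither result could be read as the question intends.

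**Working it through.** **Identification.** Let b3 and b10 be the outcome levels without any message in the top-3% and 3rd-10th percentile strata, and m3 and m10 the effects of the top-3% and top-10% messages, all on the model's scale. Then:

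- Contrast 3b = (b3 + m3) − (b10 + m10) = (b3 − b10) + (m3 − m10).
- Only m3 − m10 bears on differential response. Among messaged patients nothing separates the two terms. A stratum covariate would be collinear with the top-3% dummy. Adding controls as one further level of the wording factor would leave this contrast unchanged.
- Controls were stratified too, since the SAP stratifies within each condition. They estimate b3 and b10, so subtracting each stratum's control level leaves m3 − m10.

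**Illustration.** The plan states no power, effect size or sample size for 3b, so there is no figure to reproduce. The only input from the documents is the anticipated 56,000 primary patients (protocol, Recruitment and Enrollment). The following are assumptions: the 56,000 are the whole top 10%, so the strata split 30:70; four equal arms; 1:1 split of the two lower-stratum wordings; 50% vaccinated; no message effect; no exclusions or clustering; two-sided 5% level.

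| Stratum | Messaged | Control |
|---|---|---|
| Top 3% (16,800) | 12,600 told top 3% | 4,200 |
| 3rd-10th percentile (39,200) | 14,700 told top 10%; 14,700 told high | 9,800 |

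- Direct contrast: SE = √[0.25 × (1/12,600 + 1/14,700)] = 0.61 points.
- Chance of significance at baseline gap d, from P(|Z + d/SE| > 1.96): 5% at d = 0, 38% at 1 point, 91% at 2 points. A simulated logistic contrast gives the same percentages.
- With the wording split varied from 1:2 to 2:1, vaccination 30-70% and exclusions 0-20%: 26-48% at 1 point and 76-97% at 2 points.
- With half the sample (28,000, 50% vaccinated): 21% and 64%.

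**Control-referenced alternatives, same assumptions.**

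- Restricted to top-3% and top-10% messaged patients: SE = √[0.25 × (1/12,600 + 1/14,700 + 1/4,200 + 1/9,800)] = 1.10 points. Detectable at 80% power: 2.80 × 1.104 = 3.1 points (2.8-3.6 over the ranges above).
- Pooled, with all lower-stratum messaged patients: SE = √[0.25 × (1/12,600 + 1/29,400 + 1/4,200 + 1/9,800)] = 1.06 points. Detectable: 2.80 × 1.065 = 3.0 points (2.7-3.3).
- Simulated rejection with no message effect stays at about 5% for both at stratum gaps of 0 to 3 points.

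**What each alternative is exposed to.**

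- Restricted: suppose the wording was not randomly allocated and top-10% patients were 2 points above high patients at baseline, with controls at their mean. The bias is 2/2 = 1 point; 1/1.104 = 0.91 SE; rejection about 15%.
- Pooled: suppose the two wordings differ in effect by 2 points. At a 1:1 split the pooled interaction departs from the restricted one by 2/2 = 1 point; 1/1.065 = 0.94 SE; rejection about 16% when the restricted interaction is truly zero.

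The two hazards are nearly equal in size. They differ in kind: the first is bias, the second is a different estimand.

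**The case against.** The strongest reply is that the plan already holds the remedy. The exploratory risk-level moderator of Analysis 1 is control-referenced and removes a baseline gap on the model's scale. That is true, but it is exploratory and not tied to 3b, which would still be answered from the direct contrast. It also pools the top-10% and high wordings, so it drops 3b's own condition that the phrasing be numeric in both groups. The framing moderator of Analysis 2 uses message groups only and so has no controls.

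A second reply is that risk level in 3b means the patient's actual stratum, not the number stated. The SAP does use the term that way in its exploratory section. The ambiguity is real but does not rescue the contrast: without controls it mixes baseline uptake with response on either reading.

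A third is that everything numerical here is hypothetical. That stands. No stratum gap, vaccination rate, arm ratio or wording split is in the documents. Question 3 names no outcome, and flu diagnosis is not illustrated. The figures show how sensitive 3b would be to a gap, not that one exists.

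The consequence is also limited: 3b is not among the protocol's two research questions.

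A reader might infer that all of Question 3 fails. The documents do not support that. Contrast 3a lies within one stratum. Neither document says how its two wordings were allocated, although the SAP calls them conditions, which leans towards assignment.

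**Conclusion.** The point holds for contrast 3b. As written, it cannot support a claim that patients responded differently because of risk level, whether that means the number stated or the stratum. This follows from the allocation of wordings and the model named, and needs no numerical assumption.

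The size is unknown. Under the assumptions listed, gaps of 1 and 2 points would give a significant 3b about 38% and 91% of the time with no message effect at all.

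Two stronger readings should be resisted. One is that 3b is known to be biased, or biased in a known direction; the documents give no stratum rates. The other is that the trial's main comparisons are affected; Analyses 1 and 2 compare randomised arms and do not have this confounding. The matter should be fixed because 3b is listed as primary and worded causally, but the damage is confined to it.

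**What to change.** Make a dated SAP amendment that says whether outcome data had been seen. This matters because the messages had already gone out and an interim analysis was planned.

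1. Label the direct top-3% versus top-10% contrast descriptive, and report beside it the stratum difference among controls (SE √[0.25 × (1/4,200 + 1/9,800)] = 0.92 points in the illustration).
2. Base any inference about differential response on a message-versus-control by stratum interaction, with controls from both strata, and name which form is used.
   - The form restricted to top-3% and top-10% messaged patients keeps 3b's condition of numeric phrasing. It needs the top-10% versus high wording to have been randomly allocated, and the SAP should state how that was done.
   - The pooled risk-level moderator of Analysis 1 is valid whatever that allocation was. It asks how response to any risk message varies by stratum, and should not be labelled the answer to 3b.
3. Word either result as a between-stratum difference in response, not as an effect of the stated number.

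The pooled model is already planned, and no data beyond the planned extraction are needed. The cost is precision: under the same assumptions the SE rises from 0.61 points to 1.10 (restricted) or 1.06 (pooled). The difference detectable at 80% power rises from about 1.7 points (2.80 × 0.607) to about 3.

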### Exclusion Criteria:

• Same as primary target population

> **Recruitment and Enrollment.** All patients meeting the primary target population criteria will be enrolled into one of the 4 experimental conditions. Anticipated enrollment number for this primary target population is 56,000. Only patients from this primary target population will be contacted. However, health record data will be accessed to assess secondary outcomes for household members of this target population (expected N of 234,000) and for patients whose risk scores were calculated by Medial's ML algorithm and determined to fall just below the high-risk cutoff (expected N of 56,000). This brings the total planned enrollment to 346,000 participants.

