Because this intervention is timed to the 2020–21 flu season, the intervention period will begin ~9/1/20 and last for three months. During that period, all identified primary target population participants will be randomized and will receive 1–3 separate messages (content based on their assigned condition) in sequence via postal letter, SMS, and patient portal modalities, using all modalities available for each participant. Outcomes will be measured as of 5/31/21. Data extraction from the EHR, data cleaning, data analysis, and manuscript preparation will begin on or after 6/1/21 and will include data from not only the primary target population but also the two secondary populations.

> The primary study outcomes will be the rates of flu vaccination and flu diagnoses during the 2020–21 season (start of intervention through 5/31/21) by the primary target population. We will also measure secondary, exploratory outcomes: Rates of flu vaccination and diagnoses by fellow household members of targeted patients; rates of flu vaccination and diagnoses by non-targeted patients who were assigned a risk score that fell just below the cutoff of targeted patients; rates of flu complications and flu-like symptoms among targeted patients, household members, and those at sub-threshold risk; and rates of other relevant healthcare utilization outcomes such as ER visits and hospitalizations.

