#### Data Sources

In order to identify patients in the primary target population, Business Intelligence & Advanced Analytics (BIAA), working with Geisinger's Phenomics and Clinical Data Core (PACDC), will provide a list of patients (including patient identifiers such as Medical Record Number) that were assessed by the Medial and each patient's associated risks.

We will also obtain contact information (address, phone number, email address) to message participants in the primary target population from BIAA & PACDC.

After the intervention is complete, we will obtain experimental outcome data for all 3 population groups from BIAA & PACDC. This will include data on patient flu vaccination, diagnosis of flu, diagnosis of flu-like symptoms, presence of flu-associated complications, hospital visits, and emergency department visits. This data set will additionally include patient characteristics that will be useful as analysis covariates, such as: age, patient primary care provider, and flu-related behavior and outcomes during previous flu seasons.

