## STUDY DATA DETAILS

Data Management Procedures and Confidentiality. All data will be electronic. Datasets with identifying information will only be stored on Geisinger-managed, password-protected computers of the data brokers ([name], [name], and [name]) for the purpose of linking datasets from different sources.

A limited data set containing dates of service and ZIP codes will be shared with any non-Geisinger collaborators (e.g., Additional Principal Investigator [name] and his team) under a Data Use Agreement in compliance with HIPAA's Privacy Rule, and using data security protocols reviewed and approved by the Geisinger Security Office, Privacy Office, and Information Technology department.

After all data have been linked in a de-identified, coded file and analyzed, the datasets with identifiable information and any codes needed to link the identifiable information will be deleted. After the de-identified data have been fully analyzed, the de-identified dataset will be shared along with publications from this study. The deidentified data will not be destroyed or removed after any prespecified period of time has elapsed. We intend to permanently and securely archive the deidentified dataset at a research repository such as Open Science Framework (OSF) in order

> to be consistent with the best practices for open and reproducible science, as well as our obligation to the public as NIA-funded researchers.

The only study team members who will have access to identifiable and protected health information will be the data brokers: [name], [name], and [name]. Our non-Geisinger collaborators will have access to a limited data set which includes de-identified data as well as dates of flu vaccination and diagnosis. The remaining investigators will have access to the de-identified, coded data during data analysis.

We will analyze the data using standard behavioral research analysis methods, including computing bivariate correlations, using generalized linear models, using non-parametric models for non-normally distributed data, and entering variables as independent predictors in regression models to attempt to predict desired outcomes.

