Encouraging Flu Vaccination Among High-Risk Patients Identified by a Machine-Learning Model of Flu Complication Risk

NCT04323137

January 8, 2021

Statistical Analysis Plan

Project Status

All intervention messages have been disseminated. Data collection is ongoing, but an interim data analysis step will be conducted to inform COVID-19 vaccination efforts.

Planned Analyses

Primary Analyses:

Question 1: Does informing patients that they are at high risk for flu complications (a) increase the likelihood that they will receive flu vaccine; and (b) decrease the likelihood that they receive diagnoses of flu and/or flu-like symptoms in the ensuing flu season?

Analysis 1: We will evaluate if patients who are informed about their risk status (patients who were randomized to "high risk" message groups 2, 3, or 4 in the Study Design) exhibit improved flu vaccination and diagnosis rates compared with patients who were not informed (randomized to the control condition, group 1). To assess this, we will employ a generalized linear model with a binary distribution and log-link function (i.e. a logistic regression).

Question 2: Does informing patients that their high-risk status was determined (a) by analyzing their medical records (group 3) vs. by no specified method (group 2); and (b) by an AI/ML algorithm analyzing their medical records (group 4) as opposed to via unspecified methods or human medical records analysis affect the likelihood that they receive the flu vaccine and/or diagnoses of flu and/or flu-like symptoms in the ensuing flu season?

Analysis 2: We will evaluate this using 3 logistic regression models, comparing patients in groups 2 and 3, 2 and 4, and 3 and 4. Reported p-values will be adjusted for family-wise error rate across the three comparisons using Holm's procedure.

For both analyses described above, we will first assess the intraclass correlation (ICC) for patient-visited PCPs and/or clinics; if the ICC is greater than 0.1, a mixed model will be used with this variable included as a random effect.

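### If household-member outcomes are compared by the index patient's arm using the models of Analyses 1 and 2, nothing accounts for household clustering, and standard errors are too small when outcomes within a household are positively correlated

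*SAP*

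**What the plan says.** Protocol, Detailed Study Procedures: "We will also measure secondary, exploratory outcomes: Rates of flu vaccination and diagnoses by fellow household members of targeted patients". The same section says that the data work "will include data from not only the primary target population but also the two secondary populations", and Data Sources says "we will obtain experimental outcome data for all 3 population groups". Recruitment and Enrollment expects 56,000 primary-population patients and 234,000 household members. Only the former are randomised and contacted; Study Population says the secondary populations receive no intervention and are included for analysis only.

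SAP, Secondary Analyses, gives one rule for secondary outcomes: it will "use the approaches in Analyses 1 and 2 to evaluate the impact of the intervention on the secondary outcome measures listed in the pre-registration". Analysis 1 is a logistic regression of informed versus control patients. Analysis 2 is three pairwise logistic regressions with Holm's adjustment. One provision for dependence applies to both: "we will first assess the intraclass correlation (ICC) for patient-visited PCPs and/or clinics; if the ICC is greater than 0.1", a mixed model with that variable as a random effect is used.

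The SAP does not mention household members. The protocol's methods list (Study Data Details) includes "using generalized linear models, using non-parametric models for non-normally distributed data, and entering variables as independent predictors in regression models" and names no method for clustered data. Neither document says which arm a household member is analysed under.

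**The concern.** Household members are not randomised, so comparing them by arm means borrowing the arm of the index patient. In a household with one index patient, every member then carries the same arm, and for these outcomes treatment is assigned by household. Household members may well resemble one another in whether they are vaccinated or diagnosed with flu. A logistic regression that counts them as independent then overstates the information in the sample.

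At stake are confidence intervals that are too narrow and a false-positive rate above nominal for any claimed spillover of the messages to the household. The large sample does not protect against this, because the understatement depends on household size and correlation and not on the total number of people. Holm's adjustment does not help either, since it starts from p-values that are already too small.

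**Working it through.** **Inputs from the documents.** Expected index patients 56,000; expected household members 234,000; expected sub-threshold patients 56,000. The protocol's total reproduces: 56,000 + 234,000 + 56,000 = 346,000. Members per index patient: m = 234,000/56,000 = 4.18. This is a ratio of two anticipated counts, not an observed household size, so m = 3 and m = 2 are shown as well.

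**Assumptions.** The documents give no household ICC and no significance level. I use ICC = 0.02, 0.05, 0.1 and 0.3 and a nominal two-sided 5% test, with one index patient per household and equal household sizes.

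**Formulas.** Design effect DEFF = 1 + (m − 1) × ICC. True SE divided by reported SE = √DEFF. Actual type I error = 2 × [1 − Φ(1.96/√DEFF)].

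Worked case, m = 4.18 and ICC = 0.1: DEFF = 1 + 3.18 × 0.1 = 1.32; √1.32 = 1.15; 1.96/1.148 = 1.707; type I error = 8.8%.

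| ICC | DEFF (m = 4.18) | SE ratio | Type I, m = 4.18 | Type I, m = 3 | Type I, m = 2 |
|---|---|---|---|---|---|
| 0.02 | 1.06 | 1.03 | 5.7% | 5.5% | 5.2% |
| 0.05 | 1.16 | 1.08 | 6.9% | 6.2% | 5.6% |
| 0.1 | 1.32 | 1.15 | 8.8% | 7.4% | 6.2% |
| 0.3 | 1.95 | 1.40 | 16.1% | 12.1% | 8.6% |

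At ICC 0.001 and m = 4.18, type I error is 5.04%, which is negligible.

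**Where it starts to matter.** A type I error of 7% corresponds to DEFF = 1.170. Solving ICC = 0.170/(m − 1) gives about 0.054 for m = 4.18, 0.085 for m = 3 and 0.17 for m = 2.

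**Does the PCP/clinic rule cover it?** It may not be triggered. If it is, the random effect absorbs only the correlation shared across a PCP or clinic. Suppose the clinic ICC is 0.11 and household members share a clinic. The residual household ICC is (household ICC − 0.11)/(1 − 0.11). Household ICCs of 0.15, 0.2 and 0.3 leave 0.045, 0.101 and 0.213. At m = 4.18, DEFF is then 1.14, 1.32 and 1.68, and type I error is 6.7%, 8.8% and 13.0%, against 10.7%, 12.5% and 16.1% without the random effect.

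**Households with two index patients.** The result depends on the rule for assigning an arm, which is not written. As an illustration, attach each member at random to one of two independently randomised index patients, with a share q of members in such households: DEFF = 1 + (m − 1) × ICC × (1 − q/2). At m = 4.18, q = 25% gives 5.6%, 6.6%, 8.3% and 14.8%; q = 100% gives 5.4%, 5.9%, 6.9% and 10.7%.

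**Check by simulation.** This used 4,000 single-index households of size 1 + Poisson(3.18), a 3:1 split of informed to control (assumed), a beta-binomial outcome at 50% prevalence and 4,000 runs per setting. The unadjusted test rejected in 4.9%, 5.5%, 9.1% and 17.8% of runs at ICC 0, 0.01, 0.1 and 0.3. With household cluster-robust standard errors the rate stayed between 4.4% and 5.1%. A lower prevalence, as might apply to flu diagnosis, was not simulated.

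**The case against.** The strongest reply is that the documents do not commit to this analysis. The SAP's rule covers the outcomes in a pre-registration that is not supplied, and its wording for Analysis 1 concerns randomised patients, so the model must be adapted before it can be used for household members at all. The protocol's methods list is open-ended, and its silence on clustering is weak evidence. All of this stands, and it makes the point conditional. It does not remove it: the protocol calls these outcomes secondary, and the SAP's only rule for secondary outcomes carries no household provision. If the rule does not cover them, a planned comparison has no stated model.

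It is also fair that the size rests on assumed ICCs and on a ratio that is not a household size. A reader might infer that the bias is material from an ICC of about 0.05 in general. That holds only with about four members per index patient; at ICC 0.05 the error is 6.2% with 3 members and 5.6% with 2.

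A reader might also infer that clustering will be impossible because "the datasets with identifiable information and any codes needed to link the identifiable information will be deleted". The text does not support this. Deletion comes after the data are linked in a coded file and analysed, it concerns codes that lead back to identifiable data, and nothing says the coded file will lack a household code.

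**Conclusion.** The point holds in conditional form. If household-member outcomes are compared by the index patient's arm with the models of Analyses 1 and 2, the standard errors are too small in single-index households whenever outcomes are positively correlated. The loss ranges from trivial (about 5.0% actual error at ICC 0.001) to substantial (16.1% at ICC 0.3 with 4.18 members, 8.6% with 2). Where index patients in one household are in different arms, a member's arm is undefined and the size of the bias depends on the rule chosen.

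A reader should not extend this to the trial's main results. The primary analyses compare individually randomised patients and are not affected by it, nor is Question 3. These are exploratory outcomes, but the correction is cheap enough that it should be made. Confidence is medium, because the link to the SAP's rule is inferred and the household ICC is unknown.

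**What to change.** Add to the SAP's Secondary Analyses:

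- For any arm comparison of household-member outcomes, use household-level cluster-robust standard errors or GEE with household as the cluster, whatever the PCP/clinic ICC turns out to be.
- State that members are analysed by the index patient's arm, and fix in advance a rule for households holding index patients in different arms, for example with a sensitivity analysis limited to single-index households.
- Include a coded household ID in the de-identified analysis file.

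The cost is a few lines of text, one option in the model call and one variable taken from the household link already needed to identify these people. Design and data collection do not change. Intervals for these exploratory outcomes become wider where households are correlated (by 3% at ICC 0.02 and 15% at ICC 0.1 with 4.18 members) and hardly change where they are not.

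### The exploratory time-to-shot analysis keeps only vaccinated patients, so a change in who gets vaccinated can pass for a change in timing

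*SAP*

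**What the plan says.** The SAP, under Exploratory Analyses, Impact on timing of shot, restricts the sample: "This analysis will focus on the subgroup of patients who were vaccinated". Within it, "We will employ linear regression models to compare the time it took to receive a flu shot", first for informed patients against control and then among the three message arms. Days are counted from 21 September 2020 in every arm. If the times are too skewed for linear regression, "data will be log transformed or analyzed using a gamma model".

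Two other places define what that subgroup is. The Protocol, Detailed Study Procedures, states: "The primary study outcomes will be the rates of flu vaccination and flu diagnoses". SAP Question 1 asks whether telling patients of their risk will "increase the likelihood that they will receive flu vaccine".

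The SAP contains no time-to-event method, no timing comparison that keeps unvaccinated patients, and no caveat about selection. Its Analysis Exclusion Criteria remove deceased patients and those vaccinated before the start, which is a separate matter.

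**The concern.** Randomisation makes the arms comparable as randomised. It does not make the vaccinated patients in one arm comparable with those in another when the intervention may change who is vaccinated.

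Suppose messages persuade some patients who would otherwise have gone without a shot, and these patients tend to come late in the season. The messaged arms' mean day of vaccination then rises, although every patient who would have been vaccinated anyway came on the same day as before. The analysis would show a delay when the only change was extra people protected. If the added vaccinees come early, it shows a false speed-up. The log or gamma fallback deals with the shape of the distribution and leaves the sample as it is.

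The heading presents the result as an impact of the messages on timing. Analysis 1 will show whether uptake differed, but not whether the added vaccinees differ in timing, so it cannot rule the problem out once uptake has risen.

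**Working it through.** The documents state no figure for this analysis, so there is none to reproduce. The check asks how large a purely selective difference could be.

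**Inputs from the documents.** 56,000 patients in four arms (Protocol, Recruitment and Enrollment; Detailed Study Procedures). Time starts on 21 September 2020 (SAP), and "Outcomes will be measured as of 5/31/21" (Protocol), which gives 252 days.

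**Assumed inputs.** Equal allocation, so 14,000 control and 42,000 messaged. Control uptake p, added fraction e, timing gap L in days between added vaccinees and those vaccinated either way, and SD of days to shot. Messages only add vaccinees and move nobody else's date. Tests are two-sided at 5%; the SAP attaches no threshold to this analysis.

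**Formulas.**
- Share of messaged vaccinees who are added: e/(p+e)
- Spurious difference in means: e·L/(p+e)
- SE: SD × √[1/(14,000p) + 1/(42,000(p+e))]

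**Base case: p = 0.50, e = 0.02, SD = 30.** The added share is 0.02/0.52 = 3.8%. SE = 30 × √(1/7,000 + 1/21,840) = 0.412 days.

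| L (days) | False difference (days) | z | Chance of p<0.05 |
|---|---|---|---|
| +30 | 0.02×30/0.52 = +1.15 | 2.80 | 80% |
| +15 | +0.58 | 1.40 | 29% |
| +10 | +0.38 | 0.93 | 15% |
| −20 | −0.77 | −1.87 | 46% |
| 0 | 0 | 0 | 5% |

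With e = 0 the difference is also 0 and the rate 5%.

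**Range.** Over p 0.3–0.7, e 0.01–0.03, L 15–30 days in either direction and SD 30–40:
- Smallest (p = 0.7, e = 0.01, L = 15, SD = 40): 0.01×15/0.71 = 0.21 days, 7.4%.
- Largest (p = 0.3, e = 0.03, L = 30, SD = 30): 0.03×30/0.33 = 2.73 days, 99.9%.

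**Among message arms.** The same formula applies with 14,000 per arm, where e is the uptake difference between two arms. With p = 0.50, e = 0.01, L = 30 and SD = 30: 0.01×30/0.51 = 0.59 days, SE = 30 × √(1/7,000 + 1/7,140) = 0.505, z = 1.17, 21% before any multiplicity adjustment. If the arms have equal uptake, there is no bias.

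**Simulation.** 2,000 runs with p = 0.50, e = 0.02, gamma times with assumed mean day 40 and SD 30 for patients vaccinated either way, and no deaths. It compares the vaccinated-only difference with the difference in mean days unvaccinated over all patients to day 252; the percentage is how often each reached p<0.05.

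| Scenario | Vaccinated only (days) | All patients (days) |
|---|---|---|
| L = +30 | +1.15 (78%) | −3.6 (93%) |
| L = +15 | +0.58 (28%) | −3.9 (97%) |
| L = −20 | −0.77 (46%) | −4.6 (99.5%) |
| L = 0 | 0.0 (5%) | −4.2 (98%) |
| e = 0 | 0.0 (5%) | 0.0 (6%) |

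Check of the first row: −0.02 × (252 − 70) = −3.64 days. In that row, patients as a group spend less time unvaccinated while the planned analysis shows a delay.

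**The case against.** The strongest reply concerns weight. The analysis is labelled exploratory, the subgroup is stated openly, and a shift of about a day changes no stated conclusion. That stands, and it limits how much the point matters.

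The 80% figure also depends on a 30-day gap, a full SD. Milder assumptions give much less. At 50% uptake and SD 30, a 10-day gap gives 15% with 2 points added and 8% with 1 point; a 30-day gap with 1 point gives 30%. A 30-day gap with 2 points and SD 40 gives 56%. These rates include the nominal 5%. So the mechanism is certain, but its size in this trial is not.

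The all-patient measure answers a different question, combining whether and when. It stays near −4 days for every L tabulated, so it largely follows uptake and overlaps with Analysis 1. It also depends on the horizon. If the interim cut fell on the SAP date, 8 January 2021 (day 109), a simulation of the 30-days-later case gives −0.8 days, detected 56% of the time. The opposite signs therefore do not show that either number is miscalculated. They show that the vaccinated-only difference cannot be read as the effect of messages on timing, and the objection leaves that intact.

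**Conclusion.** The concern holds. As written, the timing analysis conditions on a post-randomisation event that is itself a primary outcome, and nothing else in the SAP corrects for it. Bias needs two conditions: uptake differs between the arms compared, and the added vaccinees differ in timing. If either fails, there is none.

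Under the assumed ranges the false difference is 0.21 to 2.73 days, in either direction, with a 7% to 99.9% chance of p<0.05. Smaller timing gaps would give less. The shifts are small in days and reach significance because the trial is large. Primary conclusions are untouched, so this is a change that should be made to one exploratory analysis.

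**What to change.** Make the timing analysis a comparison by arm of all randomised patients who remain after the SAP's exclusions.

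- Plot cumulative vaccination by arm from 21 September 2020 to 31 May 2021, or to the interim data cut, with death during follow-up as a competing event.
- Report the arm difference in mean days unvaccinated to the end of follow-up, with the horizon stated, and the proportion vaccinated by calendar dates fixed in advance.
- A Cox model may be added, with a check of proportional hazards, because messages go out "in sequence via postal letter, SMS, and patient portal modalities" and the effect may vary over the season.
- State that the estimate is the effect on time to vaccination in everyone, whether and when combined.
- Keep the vaccinated-only regression as a descriptive result, with a sentence on selection.

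The cost is SAP wording and standard code on the same vaccination dates, plus dates of death, which are not among the outcome data listed in the Protocol under Data Sources. The drawbacks are overlap with Analysis 1 and that timing among patients who would be vaccinated anyway is still not isolated.
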